2.4.1.1 Core Binding Factors

The clinical and molecular heterogeneity of AML brings about varied response to induction chemotherapy, as well as drug resistance and disease relapse. The current risk-stratification systems (such as ELN-2017 and NCCN-2018) classify AML into favorable, intermediate, and adverse risk categories based on therapeutic sensitivity to standard chemotherapeutic approaches and likelihood of sustained remission after induction and consolidation. Core-binding factor (CBF) AML is a favorable risk AML category characterized by t(8;21)(q22;q22) and inv(16)(p13;q22)/t(16;16)(p13;q22) abnormalities, and despite mutational and cytogenetic heterogeneity among t(8;21) and inv(16), these entities share similarities in prognosis, are grouped together, and managed similarly (Appelbaum *et al.*, 2006). In patients in favorable risk AML (Othus *et al.*, 2014) treated with conventional chemo induction, clinical trial data have reported CR and long-term survival rates approaching 80-90% and 50-65%, respectively (Paschka *et al.*, 2018; Schiller, 2005). Unlike the case with the favorable risk AML, intermediate

and adverse risk categories represent a particularly hard-to-treat disease population characterized by lower remission rates, high early mortality, and early relapse and death. Analysis and interpretation of outcomes between newer treatment approaches and traditional cytotoxic chemotherapy in AML must therefore be within the context of the underlying AML risk status. Therefore, we use CBF (by karyotype or FISH) as a stratification factor to account for heterogeneity in outcomes based on AML risk status.

Some patients with AML require initiation of therapy quickly after diagnosis, and full metaphase karyotype results in some centers can take 2-3 weeks to result. To avoid this issue being an impediment to accrual to study or to cause unwanted delays in initiation of therapy in patients who need fast initiation of therapy, we will allow use of karyotype and/or FISH results (as well as FLT3 results) on samples from blood or marrow that were obtained up to 3 weeks before signing consent for purposes of eligibility and stratification. In any case, results from FISH or karyotype should show if CBF abnormalities are present by at time of randomization as the presence of CBF abnormalities is a required stratification factor.

24.1.2 2.4.1.2 *FLT3* Mutations

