7.1.1 Induction therapy phase

Eligible patients will be randomized before proceeding to 7+3, or within one week of starting 7+3 in 1:1 ratio, to 7+3 alone or 7+3+ Pembrolizumab (MK-3475). As shipment of pembrolizumab to site can only be ordered after randomization, every effort should be done to randomize the patient as soon as possible. See Section 9.1 for agent ordering information. If patient is randomized after initiation of 7+3 therapy, the patient should continue to meet all eligibility criteria up to randomization date. Planned stratification factors include 1) age (younger than 65 vs. 65 and older), 2) cytogenetics **by FISH or metaphase karyotype** (presence vs. absence of core binding factor inversions and translocations), and 3) **t- AML or AML arising from prior/antecedent MDS (yes/no)**. All patients will receive cytarabine at 100 mg/m²/day continuous infusion on Days 1-7 and either idarubicin 12 mg/m²/day IV on Days 1-3 or daunorubicin 60 mg/m²/day IV on Days 1-3. A bone marrow biopsy on Day 14 (between Days 14 and 21) will be performed to assess for chemoablation. If patients have evidence of residual leukemia (defined as per institutional practice) in their bone marrow and following assessment by repeat transthoracic echocardiography (TTE) for assessment of ejection fraction, they will receive re-induction 5+2 chemotherapy, which means patients will receive cytarabine at 100 mg/m²/day continuous infusion on Days 1-5 and either idarubicin 12 mg/m²/day IV or daunorubicin 60 mg/m²/day IV on Days 1-2. Anthracycline dosing adjustments may need to be made, per institutional guidelines. Regardless of chemoablation status, on Day 8 of the induction chemotherapy and Q3W (±3 days) thereafter, half of the patients will receive Pembrolizumab (MK-3475) IV (intervention arm). The other half will not receive Pembrolizumab (MK-3475) (control arm). At time of count recovery, defined as platelet count more than 50,000 or neutrophil count more than 500, patients will undergo a bone marrow aspirate/biopsy in order to assess for response and MRD. If there is no count recovery, a bone marrow will have to be performed by day 42. If the bone marrow shows hypoplasia and patient remains without count recovery, a bone marrow will be performed q 2 weeks (+/- 3 days) till there is count recovery or evidence of persistent AML. If patients have a CR or a CRi, patients will continue with consolidation therapy. If patients do not achieve a CR or CRi, they will be taken off study. If Pembrolizumab is discontinued for any reason (after at least one dose of Pembrolizumab, the patient should continue on 7+3 or Re-Induction on study.

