10 STATISTICAL CONSIDERATIONS

10.1 Study Design/Endpoints

This is an open label, randomized, phase 2 study. The study will consist of an induction, consolidation, and maintenance phase of therapy. A total of 50 patients will be included (25 patients in the intervention arm and 25 patients in the control arm).

Induction chemotherapy for AML has been demonstrated to result in MRD negative CR (not just CR) in about 50% of patients treated (Freeman *et al.*, 2013). Few large data sets of MRD negative CR exist across different subpopulations. We hypothesize that the addition of MK-3475 (pembrolizumab) to induction chemotherapy will lead to a 25% improvement of MRD negative CR/CRi after induction and one cycle of consolidation therapy compared to 7+3 and one cycle of consolidation chemotherapy alone. We expect a response rate of 75% in the intervention arm and 50% in the control arm for patients completing their respective treatments. Using intention-to-treat analysis, in open label study, with 25 patients in the intervention arm and 25 patients in the control arm and a significance level of 0.1, we have approximately 71% power to detect an MRD-negative CR/CRi response rate difference of 25% using a one-sided Z-test for two proportions.

Early safety schedule change: After the first 6 patients have been enrolled on the experimental arm, a safety review committee comprised of the study chair, the PIs of any patient who was enrolled in the experimental arm of the trial, and a representative from CTEP will review the

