10.2 Sample Size/Accrual Rate

A total of 50 patients (25 per arm) are planned to be enrolled in the intent-to-treat analysis, which will evaluate a 25% difference in the rate of MRD-negative CR/CRi with ~71% power and an overall, one-sided alpha level of 0.1. All patients being randomized and starting induction therapy should be included in the primary analysis.

PLANNED ENROLLMENT REPORT

Racial Categories	Ethnic Categories				Total
	Not Hispanic or Latino		Hispanic or Latino		
	Female	Male	Female	Male	
American Indian/ Alaska Native	0	0	0	0	0
Asian	1	1	0	0	2
Native Hawaiian or Other Pacific Islander	1	1	0	0	2
Black or African American	1	1	1	1	4
White	15	20	1	2	38
More Than One Race	1	1	1	1	4
Total	19	24	3	4	50

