10.3 Stratification Factors

Planned stratification factors include age (younger than 65 vs. 65 and older), cytogenetics by FISH or metaphase karyotype (presence vs. absence of core binding factor inversions and translocations), and t-AML or AML arising from prior/antecedent MDS (yes/no). Dose escalation and MTD determination are not parts of this study.

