The Kaplan-Meier method and log-rank test will be used to estimate the distribution of survival between/among different marker strata. Univariate or Multivariate cox proportional hazard models will be employed to explore the significance of biomarkers on survival outcomes, while adjusting for the potential prognostic factors. The interaction effects between treatment and biomarkers also will be evaluated. Serial measurements of biomarkers will be estimated at baseline, end of induction, post-consolidation cycle 1 and 4, every 3 months during maintenance, one year, and end of treatment when applicable. Landmark analysis (Benjamini *et al.*, 1995, Dafni *et al.*, 2011) or joint modeling (Huang *et al.*, 2016) will be used to assess serial measurements of biomarkers dynamical impacts on survival outcomes, where appropriate.

Part 3: Compare the biomarkers effects between treatment arms, intensive chemo + pembro vs. intensive chemo only.

The associations between treatment arms and baseline biomarkers will be evaluated using Chi-squared test/ Fisher's exact test, ANOVA, and the Mann-Whitney U tests as appropriate. Trajectory trends of the changes in markers' values or status across the measurement time will be explored using generalized linear mixed models. The bar plots and trajectory time plots will visually show the differences over time between treatment arms. The associations between markers and the demographic/prognostic factors will also be assessed using the similar statistical methods.

Part 4: Evaluate the correlations between biomarkers.

The correlations between biomarkers will be evaluated using Pearson/Spearman rank-order correlation coefficients, Chi-squared/Fisher's exact tests, and Wilcoxon rank sum / Kruskal-Wallis tests as appropriate. A scatter plot, boxplot, and mosaic plot will also be generated for visualization. The multiplicity of the endpoints will be adjusted using the correction of Benjamini and Hochberg (Benjamini *et al.*, 1995).

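### Optional improvement, not an error: the primary Z-test leaves out the three randomization factors; adjusting for them would change power by about -1 to +3 points

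*Combined protocol and SAP*

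**What the plan says.** Three factors define the randomization strata. Section 7.1.1 begins the list with "Planned stratification factors include 1) age (younger than 65 vs. 65 and older), 2) cytogenetics", and section 10.3 repeats it: "Planned stratification factors include age (younger than 65 vs. 65 and older), cytogenetics by FISH or metaphase karyotype". Both add t-AML or AML after MDS as the third factor. Section 10.3 says nothing about using the factors in the analysis.

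Section 2.4.1.1 explains why CBF status was chosen. On how results should be read it says "outcomes between newer treatment approaches and traditional cytotoxic chemotherapy in AML must therefore be within the context of the underlying AML risk status", and it continues that "we use CBF (by karyotype or FISH) as a stratification factor to account for heterogeneity in outcomes based on AML risk status".

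The primary test appears only in the power statement of section 10.1: "we have approximately 71% power to detect an MRD-negative CR/CRi response rate difference of 25% using a one-sided Z-test for two proportions". Section 10.2 repeats the target, "which will evaluate a 25% difference in the rate of MRD-negative CR/CRi with ~71% power and an overall, one-sided alpha level of 0.1", and names no test. The one place that mentions adjustment for prognostic factors is Part 2 of the exploratory outcomes in section 10.4.2.8, where Cox models are to be used "to explore the significance of biomarkers on survival outcomes, while adjusting for the potential prognostic factors". Section 10.1 also acknowledges that "Few large data sets of MRD negative CR exist across different subpopulations".

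**The concern.** A trial that stratifies its randomization because outcome differs between risk groups usually carries the strata into the primary analysis. This plan does not, and with 50 patients and about 71% power any cheap precision is worth considering.

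Stratification balances the arms on the factors. If the factors are prognostic, that balance makes the true variance of the difference smaller than the two-proportion formula assumes. The unadjusted test then rejects too rarely under the null and gives up some power. If the factors are not prognostic, adjustment spends three degrees of freedom for nothing. What is at stake is therefore a few points of power in either direction, not validity. It also matters that one primary test is fixed in advance, because the two tests can disagree.

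**Working it through.** **Inputs from the documents.** 25 patients per arm, 50% against 75%, one-sided alpha 0.10 (sections 10.1 and 10.2); 1:1 allocation (section 7.1.1); three binary factors, hence eight strata (section 10.3). Section 13.1 counts drop-outs as not MRD-negative; this applies to both tests and favours neither.

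**The plan's own figure.** With pooled null variance and mean rate 0.625:

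Power = Φ{[0.25·√25 − 1.2816·√(2·0.625·0.375)] / √(0.50·0.50 + 0.75·0.25)} = Φ{(1.250 − 0.877)/0.661} = Φ(0.563) = 0.713.

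The exact binomial power of the same test is 0.709, and its exact size at a common rate of 50% is 0.101. The stated 71% is correct for the test named.

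**Inputs that are assumed.** The documents give no prevalence of the factors in this population and no effect on MRD-negative CR/CRi. Assumed prevalences are age ≥65 40%, CBF 10%, t-AML/MDS 25%, with permuted blocks of 4 within strata. Log-odds for (age ≥65, CBF, t-AML/MDS) are:

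- weak: −0.35, 0.6, −0.5
- CBF only: 0, 1.89, 0
- moderate: −0.7, 1.2, −1.0
- strong: −1.2, 1.6, −1.6

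In each scenario the intercept and treatment effect are solved so that the marginal rates stay at 50% and 75%.

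**Comparison.** 200,000 trials of 50 patients per scenario under each hypothesis, both tests run on the same trials. The adjusted test is ordinary least squares on arm plus three main effects, with model-based standard error and t reference, dropping a factor if one of its levels is empty.

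| Factors | Control-arm variance explained | Power Z / adjusted (%) | Change (points) | Size Z / adjusted |
|---|---|---|---|---|
| Not prognostic | 0 | 72.1 / 70.8 | −1.3 | 0.102 / 0.101 |
| Weak | 2.6% | 72.1 / 71.5 | −0.6 | 0.101 / 0.101 |
| CBF only | 5.4% | 72.1 / 72.1 | about 0 | 0.100 / 0.100 |
| Moderate | 8.9% | 72.6 / 73.5 | +0.9 | 0.095 / 0.099 |
| Strong | 18.1% | 73.5 / 76.8 | +3.3 | 0.084 / 0.097 |

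The Monte Carlo standard error of each change is at most 0.06 point. Z-test power is about 72% here, not 70.9%, because incomplete blocks leave the arms slightly unequal and the exact power of the test varies with the split; both tests face the same splits.

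**Break-even.** Scaling the moderate log-odds by 0.75 gives −0.03 point and by 0.80 gives +0.14, so the crossing is near 0.76 times moderate, where the factors explain about 5.5% of control-arm variance.

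**Sensitivity.** Over prevalences from 30/5/15% to 50/15/35% and block sizes 2 to 6, the change is −0.8 to −1.5 (not prognostic), −0.2 to −0.9 (weak), −0.8 to +0.5 (CBF only), +0.4 to +1.3 (moderate) and +2.5 to +3.9 (strong).

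**Choice of adjusted method.** A second simulation, with somewhat different prevalences and odds ratios, gave the linear model −1.0 to −1.2 (not prognostic), 0 to +0.7 (moderate, variance explained about 5 to 8%) and +1.7 to +3.9 (strong, about 12 to 20%). A Cochran-Mantel-Haenszel test over the eight sparse strata gained nothing dependable at moderate strength (−0.6 to +0.3). Logistic g-computation and logistic Wald tests gained slightly more, but their type I error reached about 11% in some scenarios. In the main runs the 95% interval from the linear model covered 94.8 to 94.9% under the alternative in all five scenarios.

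**The case against.** The strongest reply is that this is a choice between two valid tests. An unstratified test is defensible in a 50-patient phase 2 trial, and the sign of the benefit is unknown: in three of the five scenarios power falls or does not move. CBF is the only factor whose use section 2.4.1.1 justifies. The CBF-only scenario, which implies about 85% response in control-arm CBF patients and so sits close to the 80 to 90% CR rate quoted there for favorable-risk disease, shows no gain. That section also answers its own requirement by stratifying the randomization, which the plan does; it prescribes no adjusted test. Finally, a linear model for a binary outcome with a drop rule adds some fragility.

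Most of this stands, and it is why the point is optional. Two parts carry less weight. Section 2.1.1.1 gives CR rates of 60 to 70% under age 60 and 35 to 50% in older patients and those with adverse karyotypes, so an effect beyond CBF is plausible, though those are CR rates with a different age cut and do not prove it for MRD-negative CR/CRi. The fragility is modest: the drop rule was used in 0.5% of trials (7.7% if CBF prevalence is 5%), and size and coverage held with it included. The tests disagree in 3.4% to 6.4% of trials under the alternative, which is a reason to fix one as primary, whichever it is.

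**Conclusion.** The point holds as an optional improvement. The plan stratifies by three factors and names a primary test that ignores them. That test is valid and its 71% power is right. Main-effects adjustment would change power by about −1 point if the factors are not prognostic, about +1 if moderately prognostic and about +3 if strongly prognostic, with size between 0.097 and 0.101 in the main runs. The gain appears only above roughly 5 to 6% of outcome variance explained. Prevalences, effect sizes and block size are assumptions, so the direction of the change for this trial cannot be settled from the documents.

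**What to change.** In section 10.1, name one primary test: a one-sided 0.10 test of arm from a linear risk-difference model with age group, CBF status and t-AML/prior MDS as main effects, no interactions, dropping a factor if one of its levels is empty. Report the adjusted risk difference with a two-sided 95% t-interval from the model-based standard error; section 10.5.2 asks for 95% intervals without naming a method. The model-based error is preferred because a factor level holds exactly one patient in 2.8% of simulated trials (20% if CBF prevalence is 5%), and HC2 or HC3 errors are then undefined. In section 10.3, say that the factors enter the primary analysis as recorded at randomization. In sections 10.1 and 10.2, label the 71% as the power of the unadjusted Z-test, used as an approximation. Keep that Z-test as a sensitivity analysis.

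The cost is three or four sentences; the factors are already collected and the sample size does not change. The downside is a loss of up to about 1.5 points of power in these runs (allow 2) if the factors are weakly or not prognostic, and no gain if only CBF matters. A sponsor who prefers the Z-test on that ground should state explicitly that it is the primary analysis.

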toxicity data to identify any concerning drug-related safety signals before enrolling further patients on the experimental arm. We will temporarily hold enrollment in the study if two or more patients of the first evaluable six patients in pembrolizumab (MK-3475) arm develop pembrolizumab-related severe toxicity during evaluability period. The evaluability period includes the first 35 days after pembrolizumab first dose, till hematologic recovery, or till starting consolidation therapy, whichever occurs first, as defined in section 9.5.1. To be considered evaluable for purposes of the early safety rule, the patient must have received at least one pembrolizumab dose. If the true toxicity rate is 50% or greater, this rule will stop the trial with probability at least 0.89. Similarly, if the true toxicity rate is 33%, this stopping rule will end the trial with probability 0.65. In the event this occurs, the study would resume with another 6-patient cohort in which pembrolizumab dosing will start on Day 21 instead of Day 8. The patient has to receive at least one dose of pembrolizumab to be considered evaluable for safety assessment for purposes of early stopping safety rule. If the altered schedule still results in unacceptable toxicity, we will discuss alternative approaches with CTEP. No enrollment may take place until this discussion has occurred and a suitable plan has been developed.

Toxicity analysis: The first six enrolled patients will be assessed for severe toxicity in the pembrolizumab arm. In the event that severe toxicity occurs in 2 or more of the first 6 patients, the study would resume with another 6-patient cohort in which pembrolizumab dosing will start on Day 21 instead of Day 8. If the altered schedule still results in unacceptable toxicity, we will discuss alternative approaches with CTEP. A formal toxicity analysis will be conducted after 25 efficacy-evaluable patients in each study arm.

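### The 0.89 and 0.65 given for the 2-of-6 safety rule are probabilities of a temporary hold and schedule change, not of the trial stopping for good or ending

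*Combined protocol and SAP*

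**What the plan says.** All the relevant text is in Section 10.1 Study Design/Endpoints, in two consecutive paragraphs.

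The Early safety schedule change paragraph gives the action first: "We will temporarily hold enrollment in the study". The trigger for that action is set out as follows: "if two or more patients of the first evaluable six patients in pembrolizumab (MK-3475) arm develop pembrolizumab-related severe toxicity during evaluability period". To count for this rule a patient must have had at least one pembrolizumab dose. The operating characteristics follow: "If the true toxicity rate is 50% or greater, this rule will stop the trial with probability at least 0.89", and at 33% "this stopping rule will end the trial with probability 0.65". The next sentence says that if this happens "the study would resume with another 6-patient cohort", with pembrolizumab starting on Day 21 instead of Day 8. For that cohort the plan says: "If the altered schedule still results in unacceptable toxicity, we will discuss alternative approaches with CTEP". It adds that nobody may be enrolled until that discussion has produced a suitable plan.

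The Toxicity analysis paragraph restates the rule with a different denominator: "The first six enrolled patients will be assessed for severe toxicity in the pembrolizumab arm". It repeats the resumption with a second cohort.

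Section 10.6 places the trial under the ETCTN DSMB, which may recommend closing it.

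**The concern.** The rule's consequence is described in four incompatible ways: a temporary hold, a stop, an end, and a resumption. Someone could read *stop* as a pause. *End the trial* cannot be read that way when the next sentence restarts the study on the same trigger.

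These are the only probabilities that Section 10 attaches to a safety rule, so they bear on how well patients appear to be protected from a toxic combination. Taken at face value, they say that a combination with 50% severe toxicity would be stopped about nine times in ten. As written, nine times in ten it would be paused, and then at least one more six-patient cohort would be treated on the other schedule.

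The change from evaluable to enrolled patients adds a second problem. A patient who is randomized but never receives pembrolizumab cannot contribute a pembrolizumab-related event. The two versions can therefore give different decisions on the same data. This could happen in practice: under Section 7.1.1, randomization may precede 7+3 or fall within a week of starting it, drug can be ordered only after randomization, and the first dose is due on Day 8.

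**Working it through.** **Inputs.** Cohort of 6, trigger at 2 or more events, true rates 50% and 33%, stated probabilities 0.89 and 0.65, all from Section 10.1. Let X be the number of patients with a qualifying event, X ~ Binomial(n, p). Then

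P(X ≥ 2) = 1 − (1−p)^n − n·p·(1−p)^(n−1).

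**Step 1: reproduce the plan's figures (n = 6).**

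- p = 0.5: 1 − 1/64 − 6/64 = 57/64 = 0.891 (plan: 0.89).
- p = 1/3: 1 − 64/729 − 192/729 = 473/729 = 0.649 (plan: 0.65).
- p = 0.33 exactly: 0.642, so the plan evidently used 1/3.
- A trigger of 3 or more would give 0.656 and 0.320, which does not match.

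The stated pair is therefore the probability that one cohort of six evaluable patients crosses the 2-of-6 boundary.

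**Step 2: identify what crossing the boundary does.** First cohort crosses → enrollment paused → study resumes with a second cohort of six on the changed schedule → if toxicity is still judged unacceptable, enrollment is suspended and the matter goes to CTEP. No step carries a numeric criterion that ends the trial. The second step has no numeric threshold either. The probability of ending cannot be calculated from the plan.

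**Step 3: effect of the denominator.** If six are enrolled and one is never dosed, only five can contribute an event.

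- n = 5, p = 0.5: 1 − 1/32 − 5/32 = 26/32 = 0.81.
- n = 5, p = 1/3: 1 − 32/243 − 80/243 = 131/243 = 0.54.

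The number undosed is an assumption. The plan gives no expected figure.

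**Step 4: illustration for two cohorts.** Suppose, although the plan does not say so, that the 2-of-6 threshold were reused in the second cohort and that the cohorts are independent. The chance that both trigger is the product of the two tail probabilities. At 20% the tail is 1 − 0.2621 − 0.3932 = 0.345; at 10% it is 1 − 0.5314 − 0.3543 = 0.114.

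| Toxicity on the changed schedule | First cohort at 0.5 | First cohort at 1/3 |
|---|---|---|
| Unchanged | 0.891 × 0.891 = 0.79 | 0.649 × 0.649 = 0.42 |
| 20% | 0.891 × 0.345 = 0.31 | 0.649 × 0.345 = 0.22 |
| 10% | 0.891 × 0.114 = 0.10 | 0.649 × 0.114 = 0.07 |

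**The case against.** The strongest reply is that the passage largely explains itself. The paragraph is titled as a schedule change, the pause is stated before the probabilities, and the resumption comes straight after them. A careful reader would work out what 0.89 and 0.65 mean. This limits the practical harm, but it does not make *end the trial* a true description of the event.

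On the denominator, the rule's own paragraph states twice that at least one pembrolizumab dose is needed, and Section 10.5.1 starts toxicity evaluability at first pembrolizumab treatment. The enrolled version may be only a loose restatement. That is a fair reading and points to the natural correction, but the two sentences still differ and one should be changed.

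Four stronger conclusions are tempting, and the documents do not support them:

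- *The probabilities are miscalculated.* They are not. They reproduce exactly, and only their label is wrong.
- *A second toxic cohort leads to nothing more than a discussion.* Enrollment is suspended until a plan exists, and the DSMB may recommend closure.
- *The true stopping probabilities are 0.79 and 0.42.* Those values assume a reused threshold and a schedule change that does nothing to toxicity. The plan states neither, and the change is its response to toxicity.
- *Hold probabilities at lower toxicity rates are wrongly missing.* At 10% and 20% they would be 0.11 and 0.34, which is useful to report, but nothing in the plan is contradicted by leaving them out.

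**Conclusion.** Wrong as written. The figures 0.89 and 0.65 are valid probabilities that the first cohort triggers a hold and schedule change, provided six evaluable patients are in the denominator and events are independent with a common rate. They are not probabilities that the trial stops permanently or ends. The plan contains no numeric rule from which such a probability could be derived. The enrolled/evaluable mismatch is a smaller but real inconsistency: one undosed patient among six lowers the trigger probability by about 0.08 at 0.5 (0.89 to 0.81) and 0.11 at 1/3 (0.65 to 0.54).

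The two-cohort values, 0.07 to 0.79 across the cases shown, illustrate only how far any ending probability would depend on the second-cohort criterion and on toxicity under the changed schedule. The sample size and primary efficacy analysis are unaffected.

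**What to change.** In Section 10.1:

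1. Restate 0.89 and 0.65 as the probabilities of triggering the temporary hold and the pre-planned schedule change, and say that the second is computed at 1/3.
2. Reconcile the hold, stop, end and resume wording so that the rule has one stated consequence.
3. In the Toxicity analysis paragraph, replace the six enrolled patients with six evaluable patients, using the definition already given for the rule.
4. Have the sponsor state the criterion it intends for the second cohort and what follows if it is met, including whether anything ends the trial. Report operating characteristics over a range of toxicity rates under the changed schedule. The choice of threshold, schedule and consequence is the sponsor's, and none is proposed here.

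The cost is a few sentences and a small table. The price in substance is that the stated safety figures become less favourable than an 89% or 65% chance of stopping.

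### Section 10.1 runs one early safety rule on two denominators, six enrolled and six dosed patients; the stated 0.89 and 0.65 belong only to six dosed

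*Combined protocol and SAP*

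**What the plan says.** All the operative text is in protocol section 10.1, in two adjoining paragraphs.

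- **Review trigger (Early safety schedule change).** A committee reviews toxicity "After the first 6 patients have been enrolled on the experimental arm" and "before enrolling further patients on the experimental arm". The unit is the enrolled patient.
- **Hold rule (same paragraph).** Enrolment is held "if two or more patients of the first evaluable six patients in pembrolizumab (MK-3475) arm" develop severe pembrolizumab-related toxicity in the evaluability period. The unit is the evaluable patient: "To be considered evaluable for purposes of the early safety rule, the patient must have received at least one pembrolizumab dose". The one-dose condition is stated a second time later in the paragraph.
- **Operating characteristics (directly after the hold rule).** "If the true toxicity rate is 50% or greater, this rule will stop the trial with probability at least 0.89", and 0.65 at a rate of 33%.
- **Toxicity analysis paragraph.** "The first six enrolled patients will be assessed for severe toxicity in the pembrolizumab arm". The threshold and consequence follow: "In the event that severe toxicity occurs in 2 or more of the first 6 patients", the study resumes with a second cohort of six on a later pembrolizumab start. No dosing condition appears here.

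The evaluability period (sections 10.1 and 10.5.1) lasts up to 35 days from the first pembrolizumab dose and ends earlier at hematologic recovery or the start of consolidation. Nothing says what happens to the count when an enrolled patient is never dosed.

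**The concern.** This is a single decision with one threshold and one consequence, but it has two denominators. They coincide only if each of the first six patients enrolled on the arm receives pembrolizumab.

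The protocol's own procedures leave room for a difference. Section 7.1.1 allows randomisation before 7+3 or within a week of starting it, lets the drug be ordered only after randomisation, and gives the first dose on Day 8. Section 10.5.2 allows for randomised patients who received no study medication. Section 4.4 lets a registration be cancelled when no protocol therapy is given, but does not cover a patient who starts 7+3 and never reaches pembrolizumab.

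Two things are at stake. First, if the enrolled wording is followed, an undosed patient takes one of the six places and cannot contribute a pembrolizumab-related event, so a toxic schedule is less likely to trigger the hold than the protocol states. Second, a review triggered by enrolment can fall before the sixth patient has had any pembrolizumab.

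**Working it through.** **Inputs.** Threshold of 2 events, six patients, true rates of 50% and 33% (all section 10.1). An undosed patient cannot have a pembrolizumab-attributed event (section 10.5.1). The number or proportion of undosed patients is not in the documents and is varied below.

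**Formula.** With n dosed patients and true rate p,

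P(hold) = 1 − (1 − p)^n − n·p·(1 − p)^(n − 1).

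**Step 1: the protocol's own figures.**
- n = 6, p = 0.50: 1 − 1/64 − 6/64 = 57/64 = 0.891 (stated 0.89).
- n = 6, p = 1/3: 1 − 64/729 − 64/243 = 0.649 (stated 0.65). At p = 0.33 exactly the value is 0.642.

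Both stated figures are reproduced, taking 33% as one third for the second. Both require six patients who received the drug.

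**Step 2: six enrolled, fewer dosed, same threshold of 2.**

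| Dosed among six enrolled | p = 0.50 | p = 1/3 | p = 0.33 |
|---|---|---|---|
| 6 | 0.891 | 0.649 | 0.642 |
| 5 | 26/32 = 0.8125 | 0.539 | 0.533 |
| 4 | 11/16 = 0.6875 | 0.407 | 0.402 |

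With one undosed patient, the chance of missing a 50% toxicity rate rises from 1 − 0.891 = 0.109 to 1 − 0.8125 = 0.1875.

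**Step 3: averaging over an assumed non-dosing rate.** If each enrolled patient is dosed with probability q, independently of toxicity, each has an event with probability q·p. The formula then applies with n = 6 and q·p in place of p. For q = 0.90 and p = 0.50, q·p = 0.45 and P(hold) = 1 − 0.55^6 − 6 × 0.45 × 0.55^5 = 1 − 0.0277 − 0.1359 = 0.836.

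| Assumed undosed | All six dosed (q^6) | Hold, p = 0.50 | Hold, p = 0.33 |
|---|---|---|---|
| 5% | 0.735 | 0.865 | 0.609 |
| 10% | 0.531 | 0.836 | 0.573 |
| 20% | 0.262 | 0.767 | 0.499 |

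The last column uses 0.33 exactly, so its reference value with no undosed patients is 0.642.

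**The case against.** The strongest reply is that the operative rule is already clear. The hold rule names evaluable patients, the one-dose condition is stated twice for it, and the two probabilities follow it directly. Section 10.5.1 starts toxicity evaluability at the first pembrolizumab treatment. On this view the Toxicity analysis paragraph is a loose summary and no number is wrong. That much stands: six dosed patients is the likely intent, and under that reading nothing is lost.

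Three stronger readings are tempting, and the documents do not support them.

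- *The 0.89 and 0.65 are miscalculated.* They are not; both reproduce for the rule they accompany.
- *Once one of the six goes undosed, a sixth evaluable patient can never appear, so the threshold is applied to five or four.* The text asks for a review before further enrolment on the arm; it does not close the arm. If the review raises no concern, enrolment can resume and the next dosed patient can complete the evaluable six. No sentence expressly applies the threshold to a smaller group.
- *Toxicity would go unnoticed.* The committee looks for any concerning drug-related signal, beyond the count of two, and a DSMB oversees the study (section 10.6).

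What the reply does not remove is that two of the three sentences setting up this decision say enrolled, one of them repeating the threshold and its consequence. The rule also gives no instruction for an undosed patient. On timing, enrolment of the sixth patient can be read as the earliest point for the review instead of its date, but then the review date is simply unstated.

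**Conclusion.** The inconsistency is real and is in the current text. It is a conflict of wording in a safety decision rule, not an error of calculation. The stated probabilities hold for six dosed patients. If the enrolled wording is applied, they no longer hold once any of the six is undosed: with one undosed patient the loss is about 8 percentage points at a 50% rate (0.891 to 0.8125) and 11 at one third (0.649 to 0.539); with two it is about 20 and 24 points (to 0.6875 and 0.407).

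These losses are conditional on the enrolled wording being followed and on at least one patient going undosed. The averaged figures also rest on an assumed non-dosing rate of 5% to 20% and on dosing being independent of toxicity. The documents support no single rate, so the range should be read as a sensitivity display and not as a forecast.

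**What to change.** Reconcile the passages in section 10.1 so that one denominator applies throughout:

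1. Use the first six evaluable patients (at least one pembrolizumab dose) in the review trigger, the hold rule and the Toxicity analysis paragraph, and for the second six-patient cohort.
2. State that an enrolled patient who is never dosed is replaced in the count.
3. Tie the review to the sixth evaluable patient completing the evaluability period instead of to enrolment.

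With these changes 0.89 and 0.65 stand as written. Sections 10.5.1 and 13.1 could be aligned in the same amendment, since the first starts toxicity evaluability at pembrolizumab and the second at 7+3.

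**Cost.** The first change is wording only. The second and third make explicit design choices that the text now leaves open, and a few more patients may be assigned to the arm before the review. That number cannot be given because section 10.2 states no accrual rate, but it can be limited to one replacement per undosed patient.
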